1.1.2 Secondary Objectives

- To evaluate ⁶⁸Gallium-DOTATATE uptake in NETs and its association with tumor differentiation.
- To determine whether ⁶⁸Gallium-DOTATATE uptake value is predictive of tumor growth and/or disease progression.
- To determine the relation between somatostatin receptor status in tumor samples and ⁶⁸Gallium-DOTATATE uptake.
- To evaluate the feasibility of radio-guided surgery in NETs using ⁶⁸Gallium-DOTATATE.

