3.1.1.2 Non-invasive imaging

- CT scan with contrast of the chest, abdomen and pelvis. Tridimensional tumor measurements will be performed on contrast CT scans to evaluate size and rate of tumor growth, on scans obtained at baseline and at each follow up visit.
- Patients with a severe iv contrast allergy (anaphylaxis with premedication) will have a MRI of the abdomen and pelvis performed and non-contrast CT of Chest instead of the CT scan (MRI of chest will only be performed if suspicious lesions seen on previous imaging or on ⁶⁸Gallium-DOTATATE PET/CT).
- ⁶⁸Gallium DOTATATE PET/CT scan for gastrointestinal or pancreatic NET.

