conventional imaging studies for assessment of changes in lesions which would minimize false positives. Furthermore, in patients who require surgery, diagnosis will be confirmed by histopathology.

Based on current protocols for MEN1 and VHL and patients seen by provider on these protocols, we estimate an accrual rate of 3-10 patients per month. This includes patients with VHL and pancreatic NETs and patients with MEN1. Currently the VHL protocol includes up to 220 patients followed every year, with an accrual rate of 4 new patients on average per month [range 2-7/month in 2012]. For patients with MEN1 patients, up to 200 patients are followed on a current protocol. If we assume that 50% of those patients are willing to participate and adding the new patients recruited from outside the NIH and sporadic cases, we should reach an accrual rate between 3-10 patients per month. Hence, the total length of accrual period for this study is estimated to be 10 months to 3 years.

One of the secondary objectives of the study is to determine whether DOTATATE uptake value predicts tumor and disease progression. To study this, the SUV uptake of ⁶⁸Ga-DOTATATE on PET imaging will be compared between patients who require operative intervention and those who do not, and SUV uptake will be correlated to tumor size and growth rate of the tumors. Among patients with sporadic or familial gastrointestinal and pancreatic NET to be accrued into this study, it is expected that 10-30% of them will require operative intervention. With a targeted total of 100 patients: approximately 20 requiring operative intervention and 80 not requiring operative intervention. The study would have 84% power to detect a standardized mean difference (mean difference/SD) of 0.75 in SUV uptake of ⁶⁸Ga-DOTATATE between the two groups of patients, using the two-sample t-test at the 5% significance level. Two recent published studies [46, 62] show that the variability of SUV uptake of ⁶⁸Ga-DOTATATE is large, and the standard deviation is comparable to the mean value. If the variability of SUV uptake of ⁶⁸Ga-DOTATATE of the current study is comparable to that in those previous 2 studies, then detecting a standardized mean difference of 0.7 would be close to detecting a 1.75 mean fold change.

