7.1 AMENDMENT D

We will increase our accrual ceiling for several reasons. The initial sample size calculation was based on a non-inferiority analysis of ⁶⁸Gallium-DOTATATE PET/CT to octreoscan SPECT, the currently used imaging study to detect NETs. Our interim analysis in 50 patients shows that ⁶⁸Gallium-DOTATATE PET/CT is much more accurate than Octreoscan SPECT (overall accuracy of 78% for ⁶⁸Gallium-DOTATATE PET/CT; 60% for Octreoscan SPECT, 74% for triphasic CT scan% in a per patient analysis). Thus, the sample size calculation has been revised to determine if ⁶⁸Gallium-DOTATATE PET/CT is more accurate than CT scan. Based on the data collected, the difference in the diagnostic accuracy between these two imaging techniques is 4% and the proportion of discordant imaging results is 12%. In order to detect 5% difference between these two imaging techniques with 80% power and with 10% discordant rate, 295 patients are required. The comparison is based on McNemar's chi-squared test at the 5% significance level. Thus, we are increasing our accrual ceiling to 295 patients. In addition, in a per lesion analysis between the two imaging techniques (⁶⁸Gallium-DOTATATE PET/CT and triphasic CT), there were discordant results in 30 of the 50 subjects (in 26 patients, ⁶⁸Gallium-DOTATATE PET/CT found additional lesions, in 4 patients CT found additional lesions, 20 patients had concordant (positive or negative) results). Additional reasons to increase the accrual ceiling are: 1) the most accurate way to confirm the results and findings from ⁶⁸Gallium-DOTATATE PET/CT scan is to compare them to pathologic evaluation of resected tumors. Thus far, 21 of 84 subjects have been recommended to have surgical treatment because of metastatic disease detection on ⁶⁸Gallium-DOTATATE PET/CT, and 9 patients have had a surgical procedure with pathology confirming the results (all true positives). Therefore, in order to increase the power of this comparison, an increase in accrual would be necessary. 2) We have used a gamma probe for intra-operative detection of NETs, in two subjects the results were positive and in order to validate this technique, an increase in number of patients would be needed.

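### Section 7 studies whether uptake predicts progression through operative status and tumor size or growth rate, neither of which counts new lesions

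*Combined protocol and SAP*

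**What the plan says.** Section 1.1.2 asks whether the "uptake value is predictive of tumor growth and/or disease progression". Section 7 restates this as an aim to "determine whether DOTATATE uptake value predicts tumor and disease progression" and names two analyses for it.

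- SUV "will be compared between patients who require operative intervention and those who do not". The expected groups are "approximately 20 requiring operative intervention and 80 not requiring operative intervention", with 84% power for a standardized difference of 0.75 by two-sample t-test at the 5% level.
- "SUV uptake will be correlated to tumor size and growth rate of the tumors".

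On the data side, section 3.1.1.2 says "Tridimensional tumor measurements will be performed on contrast CT scans to evaluate size and rate of tumor growth", at baseline and at each follow-up visit. The précis provides for yearly imaging with biochemical and clinical evaluation for five years, to assess both growth and progression. Section 4.1 lists progression, stage and clinical outcome among the things to be related to tumor grade, but defines none of them. Section 7 gives no progression event, no size-change threshold and no rule for new lesions.

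**The concern.** Section 1.2 calls metastatic disease the most important prognostic factor after grade. New metastases are therefore a form of progression that this objective should detect, and neither analysis in section 7 is built to see them. Operative status reflects resectability, lesion size, symptoms and baseline staging as well as change over time. Growth rate exists only for a lesion that has an earlier measurement, so a lesion that newly appears contributes nothing.

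At stake is how the result can be read. A null finding could mean that uptake does not predict progression, or that progression was not captured. A positive finding by operative status could reflect extent of disease at entry, since the scan that supplies the predictor also contributes to the decision to operate.

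**Working it through.** **The plan's own figure.** Inputs from section 7: groups of 20 and 80, standardized difference 0.75, 5% level (two-sided assumed, as sidedness is not stated). The noncentrality is 0.75 × √(20 × 80 / 100) = 0.75 × 4 = 3.0 on 98 degrees of freedom, which gives power of 84.4%. The stated 84% reproduces. It is the power to detect a difference between operated and non-operated patients. It says nothing about how well that split represents progression.

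**What the two analyses record.** These are illustrative patients, set against sections 3.4, 7 and 7.1.

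1. Measured lesions stable, new metastases at a yearly scan, not operated on. Operative group: no. Growth rate: near zero. The progression does not register in either analysis.
2. Measured lesions stable, new metastases, operated on. Operative group: yes. The first analysis captures this patient indirectly; growth rate still does not.
3. Pancreatic lesion operated on after entry because it meets a section 3.4 size criterion, or because of symptoms, with no enlargement. Operative group: yes. There is no progression over follow-up.
4. Metastases found on the baseline study PET lead to surgery. Operative group: yes. What was found is extent of disease at entry, not change afterwards. Section 7.1 reports 21 of 84 subjects recommended for surgery on this ground (21/84 = 25%) and nine who had a surgical procedure by then.
5. Lesion seen on baseline PET but not on baseline CT, later visible on CT. It has an SUV but no baseline CT size, so no growth rate from baseline can be calculated, and its appearance on CT is not an event.

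The fifth pattern is plausible. In the per-lesion comparison of PET/CT with CT, section 7.1 says "there were discordant results in 30 of the 50 subjects", and in 26 of those PET/CT found additional lesions. That is discordance between modalities, however, and does not show how many such lesions later appear on CT.

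**Direction.** Pattern 1 puts progressing patients in the comparison group. If their SUVs resemble those of other progressing patients, this pulls the observed difference toward zero. Patterns 3 and 4 add patients without progression over follow-up to the operated group. In pattern 4 the study PET itself drives the grouping, which could create a difference in SUV even if uptake did not predict later progression. These effects need not point the same way, and the documents give no frequency for pattern 1, 3 or 5.

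**The case against.** The strongest reply has four parts.

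- **Section 7 has no progressor variable.** A reader might infer that a patient with new metastases and stable lesions is scored as not progressing. The documents do not support that: nobody is scored. What can be said is that progression has no definition in section 7 and that its two analyses do not register this patient's event.
- **Progression appears elsewhere.** The précis and section 4.1 both mention it, and section 3.2 (Follow-up examinations), whose text was not available for this check, may hold rules for reading the yearly scans. It therefore cannot be said that the whole plan lacks a definition. But the précis and section 4.1 supply none, and assessment rules in section 3.2 would not change the analyses that section 7 names for this objective.
- **New metastases are not always missed.** Sections 3.4 and 7.1 show that metastases can lead to surgery. This stands, and it narrows the gap to new lesions that are not operated on.
- **No large loss of power is shown.** A reader might assume that 20 of 100 patients progress and that half of them do so only by unoperated new lesions. That leaves 10 operated and 90 not, with 10 hidden progressors among the 90. The difference becomes 0.75 × (1 − 10/90) = 0.667, and power falls from 84% to 51%. The documents do not support this figure. Neither rate is documented. Much of the fall comes from shrinking the operated group, since a 10/90 split with the full 0.75 already gives 61%. The sample size is also out of date: section 7.1 raised the ceiling to 295 and section 7.2 to 390. With the same assumed rates, and every patient analysed, power is about 93% at 295 and 98% at 390.

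The reply thus removes the claim of scoring and the power loss. It does not give section 7 an outcome that counts new lesions.

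**Conclusion.** The point holds in a limited form. Section 7 answers the progression half of this secondary objective with a poor surrogate. Operative status misses new lesions that are not operated on, and it includes patients operated on for size, symptoms or disease already present at entry. Growth rate covers enlargement of measured lesions only. This follows from the text of sections 3.4, 7 and 7.1 and needs no assumed rate.

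The size of the bias cannot be derived, and its net direction is not established. At the current ceiling of 390 the problem is the validity of the outcome rather than power. It is worth correcting because the yearly scans that would support a better outcome are already planned. It does not touch the primary objective.

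**What to change.** In section 7, add a per-patient progression outcome assessed at each yearly visit: enlargement of a measured lesion beyond a change stated in advance, or any new lesion on the yearly CT/MRI. Analyse it against baseline SUV. Time to first progression in a Cox model is one suitable analysis, but it is not essential. Keep growth rate of measured lesions as the outcome for tumor growth, and report operative status as a separate outcome. Make the definition consistent with any assessment rules in section 3.2.

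Flag separately any lesion that was already visible on baseline PET and appears on CT only later, and report results with and without these lesions counted as new.

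The cost is a paragraph of wording and one derived variable from scans already scheduled, with no added procedure. The drawback is that readers who know the PET findings may pick up more apparently new lesions on later CTs, which is the reason for the flag.

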Furthermore, we will analyze somatostatin receptor status in tumor samples in patients who have surgical treatment using immunohistochemistry and Western blot analysis for protein expression [49] and quantitative RT-PCR for mRNA expression. Receptor status in tissue samples will then be correlated to $^{68}\text{Gallium}$ -DOTATATE PET uptake status in the same lesion, which is specific to somatostatin receptor 2 [50]. With this information on receptor status of the lesions and $^{68}\text{Gallium}$ -DOTATATE PET uptake, the feasibility of using this agent in the future for treatment of patients with metastatic NETs could also be determined.

Abbreviated Title: ⁶⁸Gallium Detecting Tumors

Version Date: 09/20/17

Additionally, we will collect research blood and urine at baseline in order to perform proteomics using Mass spectrometry for the discovery and validation of biomarkers. Recent advances have shown blood and urine markers could be identified by mass spectrometry in a variety of cancers (bladder, renal, ovarian, breast, colorectal) [51, 52]. Serum proteomics has been used to find biomarkers in gastric cancer [53], prostate cancer [54] and lung cancer [55].

As discussed previously, NETs can be functional and secrete hormones into the circulation, leading to the development of clinical symptoms. They are thought to be due to the release of serotonin and peptides. Chromogranin A is a biochemical marker in the circulation currently used for monitoring and screening of NETs. However, this marker has been shown to be in the normal range for certain patients even though they present with clinical symptoms like flushing. Moreover, we have seen patients who have marked symptoms of flushing and diarrhea but with normal levels of vasoactive hormones on our screening, which suggests there are vasoactive hormones present that are unknown. As an example, a recent study demonstrated MAC2 to be secreted by proteomes of neuroendocrine cell lines and the same marker to be elevated in seven patients with NET, and could be identified as a potential biomarker for NET [56]. With the collection of serum and urine samples for proteomic analysis in our patient cohort, we could help identify new biomarkers for the screening and monitoring of NETs that do not have elevation in known vasoactive hormones.

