4 BIOSPECIMEN COLLECTION

4.1 CORRELATIVE STUDIES FOR RESEARCH

The differentiation status (Grade 1/2/3) of the tumor lesions on pathology will be correlated with imaging findings from ⁶⁸Gallium-DOTATATE PET/CT and with disease progression, extent of disease (Stage) and clinical outcome. This will determine the predictive value of ⁶⁸Gallium-DOTATATE imaging and will provide information on the severity of disease. Pathology of the NETs will be staged according to the WHO classification for NET 2010 [14].

We will analyze somatostatin receptor expression levels and subtypes in tumor samples from patients who undergo surgical intervention by immunohistochemistry and Western blot for protein expression [49] and with quantitative RT-PCR for mRNA expression. This will be compared to ⁶⁸Gallium-DOTATATE uptake in the same lesion [50]. With this information on actual receptor status of the lesions, future feasibility of radiolabeled somatostatin treatment for metastatic NET (“peptide receptor radionuclide therapy”) could be evaluated.

Additionally, we will collect a blood sample (Red/yellow SST tube with Gel and Clot Activator additive, 2x8ml tubes for a total of 16ml) and urine sample (1 container of maximum 100mL) at baseline for each patient, in order to perform proteomics for the discovery and validation of biomarkers.

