5.1.3 Imaging Data

Extracted imaging data include:

- (1) PET imaging data will include maximal standardized uptake values (SUV) for each region of interest, correlation with the CT images of the PET/CT and, when feasible, with the IV contrast CT.
- (2) All image data will be stored on a secure server, with access limited to credentialed users. This will permit flexible numeric raw data extraction for quantitative analysis and creation of summary data reports.

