Additionally, radio-guided surgery using a gamma probe will be used for patients that require an operation and have lesions confirmed to have positive uptake on ⁶⁸Ga-DOTATATE PET/CT. The main goal is to assess feasibility of this new technique with radio-guided surgery as this approach may facilitate the intra-operative detection of some NETs or detect additional lesions. For measurements of the uptake by the probe, the count rate signal will be used as well as the ratio between the target and the background (normal tissue). Further, the sensitivity of radio-guided surgery will be compared to pre-operative ⁶⁸Ga-DOTATATE PET/CT SUV uptake and to surgical palpation for intra-operative detection of NETs. The number of lesions and their SUVs detected on PET/CT, the number detected by the gamma probe and by visualization and surgical palpation will be compared. The final histological diagnosis will be used as the gold standard for correct identification of NETs.

Another important secondary objective of the study is to determine the relationship between somatostatin receptor status (SSRT) in tumor samples and ⁶⁸Gallium-DOTATATE uptake. Based on the existing literature [49, 63], SSTR score is approximately uniformly distributed. With 20 expected patients requiring operative intervention, the study will have 82% power to detect a standardized mean difference of 1.2 between half of the patients with low SSRT-2 scores (0-1) versus the remaining patients with high SSTR-2 scores (2-3) using the two-sample t-test at the 10% significance level. The power would be less than 80% if the standard mean difference is

less than one. The relationship between subtypes of SSRT and ⁶⁸Gallium-DOTATATE uptake will also be examined, but it is expected that they have lower affinity to ⁶⁸Gallium-DOTATATE uptake than SSRT-2. As a secondary objective, the outcome will be useful in generating hypothesis and planning for future studies.

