7.3 DETAILED ANALYSIS

We recently performed an analysis of the detection rate of the 3 imaging modalities in the first 131 patients enrolled in the study for known or suspected gastrointestinal and pancreatic neuroendocrine tumors. Lesions detected on any of the 3 imaging modalities were defined as the denominator. ⁶⁸Gallium-DOTATATE detected 95.1% of lesions compared to Octreoscan SPECT, which only detected 30.9% of lesions ($p<0.0001$). Furthermore, in four out of 14 patients, ⁶⁸Gallium-DOTATATE PET/CT found a previously unknown primary tumor not detected by Octreoscan SPECT. Twenty-five patients underwent surgical resection for their primary tumors and/or metastases. An analysis of imaging concordance with histopathology showed that ⁶⁸Gallium-DOTATATE PET/CT found true-positive lesions 63.7% (72 out of 113 lesions) compared to 22.1% (25 out of 113 lesions) for Octreoscan. In assessing the impact of ⁶⁸Gallium-DOTATATE PET/CT on clinical management, ⁶⁸Gallium-DOTATATE PET/CT detected additional lesions in 93 out of the 131 patients (71.0%) compared to Octreoscan SPECT. Forty-four out of the 93 patients with additional lesions were found to have metastatic disease. These additional findings led to a change in management in 43 out of the 131 (32.8%) of patients. Given the clear imaging superiority of ⁶⁸Gallium-DOTATATE PET/CT to Octreoscan, we will no longer perform Octreoscan in patients being enrolled and will compare its accuracy to CT/MRI scanning. This will result in lower radiation exposure to subjects and reduced cost.

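### The receptor–uptake objective concerns the same lesion, but its test is planned on about 20 patients as units, and resected lesions that PET did not show are not assured an SUV

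*Combined protocol and SAP*

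**What the plan says.** Section 4.1 compares receptor expression in resected tumour with "uptake in the same lesion". Section 1.2 pairs receptor status in tissue with "uptake status in the same lesion, which is specific to somatostatin receptor 2". Both make the lesion the natural unit.

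The sizing in section 7 uses patients: "With 20 expected patients requiring operative intervention, the study will have 82% power to detect a standardized mean difference of 1.2". The comparison is made "using the two-sample t-test at the 10% significance level", and the contrast it tests is "between half of the patients with low SSRT-2 scores (0-1) versus the remaining patients with high SSTR-2 scores (2-3"). Section 7 does not say which lesion, or which summary of lesions, represents a patient with several resected lesions. It gives no within-patient correlation for this endpoint, although section 7 (accuracy) and section 7.2 (gamma probe) each use 0.2 for theirs.

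On uptake, section 5.1.3 states: "PET imaging data will include maximal standardized uptake values (SUV) for each region of interest". No section says how a resected lesion without visible uptake receives a region of interest or an SUV.

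Section 7.3 reports that, among 25 resected patients, PET found true-positive lesions in "63.7% (72 out of 113 lesions").

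**The concern.** There are two linked problems.

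**Unit of analysis.** When a patient has several resected lesions, the most direct evidence on receptor and uptake comes from comparing them with each other, because patient-level factors are then held fixed. A t-test on patients cannot use that comparison. It needs one score and one SUV per patient, and the plan does not say how either is obtained.

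**Selective missingness.** The plan itself describes the tracer as specific to receptor subtype 2, so lesions that PET misses are plausibly those with low receptor expression and low uptake. If SUVs exist only where PET showed something, these lesions leave the analysis because of the very relation being studied. The estimated association is then biased towards zero, in an analysis that sections 1.2 and 4.1 link to the feasibility of future radionuclide treatment.

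**Working it through.** **1. The plan's own power figure.** Inputs (section 7): 20 patients split 10 and 10, standardized difference 1.2, two-sample t-test, alpha 0.10. Sidedness is not stated and is taken as two-sided.

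- Noncentrality = 1.2 × √(10 × 10 / 20) = 2.68, with 18 degrees of freedom.
- Power = 82.5%, against 82% stated.

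The figure reproduces with 10 against 10 independent patients, which confirms that the patient is the unit.

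**2. Lesions per resected patient.**

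| Source | Lesions / patients | Lesions per patient (k) | Share of lesions unused if one per patient, 1 − 1/k |
|---|---|---|---|
| 7.2, planning value | – | 2 | 50% |
| 7.2, observed | 56 / 24 | 2.33 | 57% |
| 7.3, observed | 113 / 25 | 4.52 | 78% |

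These counts are upper bounds on usable pairs. Section 3.4.3 collects at least 0.5 cm per side of tissue remaining after pathology, so some small lesions may have no receptor value.

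**3. What averaging loses.** If a patient's lesions are averaged, none is dropped but within-patient variation in receptor score is removed. With k lesions and a within-patient correlation ρ of the score, the share of score variance removed is 1 − [1 + (k − 1)ρ]/k. The documents give no ρ for receptor score, so a range is assumed.

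| ρ | k = 2.33 | k = 4.52 |
|---|---|---|
| 0.2 | 46% | 62% |
| 0.5 | 29% | 39% |
| 0.8 | 11% | 16% |

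**4. Lesions that PET did not show.** 113 − 72 = 41, and 41/113 = 36.3%. This reads the remaining 41 as histologic lesions missed by PET, which is plausible but not spelled out in section 7.3.

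**5. Attenuation if those lesions have no SUV.** Assume bivariate normality, a true correlation r, and the lowest fraction p of uptakes missing.

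- Cut-point a = Φ⁻¹(p); λ = φ(a)/(1 − p); remaining uptake variance v = 1 + aλ − λ².
- Observed correlation = r√v / √(1 − r² + r²v).
- For p = 0.363: a = −0.351, λ = 0.589, v = 0.447. With r = 0.60 (illustrative, not from the documents), the result is √(0.161/0.801) = 0.45.
- Smaller losses do less: p = 0.20 gives v = 0.583 and 0.50; p = 0.10 gives v = 0.712 and 0.53.

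In two-group form, a simulation with a true standardized difference of 1.2 and the lowest 36.3% of SUVs missing lost 57% of low-score lesions but 15% of high-score lesions. The difference among the remainder was about 0.77. With 20% missing it was 0.93, and with 10% missing 1.05.

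**The case against.** **The plan never prescribes one lesion per patient.** This stands. The patient unit comes from a sizing paragraph, and a patient average would collapse pairs rather than discard them. A reader might infer that most lesion pairs are thrown away, and that lesion-level analysis would raise power at a difference of 1.0 from 69% to 91–97%. The documents do not support that. It contrasts one lesion per patient with all lesions, and it borrows the 0.2 correlation that the plan set for classification and detection, not SUV. The effective-sample-size formula behind it also holds receptor group constant within a patient. Under that assumption a t-test on patient means already reaches 90% (k = 2.33) to 97% (k = 4.52), within about one percentage point of the lesion-level result. No power gain is therefore claimed here.

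**Twenty patients is out of date.** This also stands. The figure comes from the 100-patient target; section 7.2 now seeks 85 radio-guided surgery patients. With 85 patients as units, split equally, power at a difference of 1.0 would be about 99.8%. Lack of power is thus not the main issue, but a larger cohort does not remove selective loss of low-uptake lesions.

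**Section 5.1.3 does not restrict regions of interest to visible uptake.** True: it also provides for correlation with CT. A reader might infer that all 41 lesions will lack an SUV, but the text only fails to assure one. Lesions may also be missed because of size or site rather than low receptor density, and some may yield no research tissue. The fall from 0.60 to 0.45 is therefore a worst case.

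**The objective is secondary and described as hypothesis-generating.** True, and it limits the weight of the point. Section 7 also calls it important, and an attenuated association misleads later planning too.

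**Conclusion.** The point holds as a modest improvement in method. The objective is framed within lesions, and the only analysis described for it is between patients. At 2.3 to 4.5 lesions per resected patient, averaging would remove roughly 11% to 62% of receptor-score variance over assumed within-patient correlations of 0.8 down to 0.2. Picking one lesion would set aside 57% to 78% of lesions on the observed counts.

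The missing SUV rule is the more lasting weakness. Up to 36% of histologic lesions could be affected, and their loss would bias the association towards zero whatever the sample size. The bound of 0.60 to about 0.45 rests on bivariate normality, an illustrative true correlation, and exactly the lowest 36% being absent; smaller or less selective losses do less harm. The stated 82% power is arithmetically correct and is not in dispute.

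**What to change.** - **Section 7.** Make the resected lesion the unit. Regress log SUVmax on receptor score with a random intercept for patient, or use patient-clustered standard errors.
- **Section 5.1.3.** For each resected lesion that has receptor data but was not visible on PET, read an SUVmax from the stored images at its co-registered CT or operative site. List lesions that cannot be placed, and add a sensitivity analysis treating them as low or censored uptake.
- **Sizing.** Restate the detectable effect using the number of operated patients now expected and an assumed range of within-patient correlation for SUV, noting that lesion counts are upper bounds on usable pairs.

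The cost is plan wording and some re-measurement of images that section 5.1.3 already keeps for numeric extraction; no new patients, scans or procedures are needed. The drawback is imprecise placement for small lesions, which the listing and sensitivity analysis make visible. The change should be made before the receptor analysis is run.
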